If the participant has not performed an activity, determine if it was not performed due to health reasons or non-health reasons. You may need to ask whether s/he found it too difficult or unsafe to perform the activity (Did Not Perform: Health), or whether s/he did not have the opportunity or preferred not to do the activity (Did Not Perform: Non-health).

Post-Fracture Physical Activities of Daily Living (PADLs)

[all 16 items]

In this group of questions, I am interested in whether you had help in performing each of these activities.

By "help" I mean whether you used some device or equipment or the help of another person, to do the activity. Let me first give you some examples of what I mean when I ask whether you used equipment.

- To get dressed, some people use special dressing sticks or shoe horns.
- In the bathroom, raised toilet seats, bath seats, and grab bars in the toilet or tub are sometimes used.
- To reach things, you might use long-handled reachers.

Basically, I am interested in whether "in the past week" you used any devices or help from another person to perform these activities.

In the PAST WEEK, ON AVERAGE, did you use help to....

	No Help 0	Used Equip 1	Used Human Assist 2	Used Equip & Human Assist 3	Didn't perform: Health 4	Didn't perform: Non-health 5	Don't Know 7	Refused 8
q. Walk 10 feet or across a room								
If 1 or 3 selected indicate type of equipment 1=Cane(s)  2=Walker  3=Wheelchair  4=Crutches  5=Other 								
r. Walk one block on a level sidewalk								
If 1 or 3 selected indicate type of equipment 1=Cane(s)  2=Walker  3=Wheelchair  4=Crutches  5=Other 								
s. Climb 5 stairs								
t. Get into car								
u. Get in and out of bed								
v. Rise from an armless chair								
w. Put on a shirt/blouse								

x. Button a shirt/blouse								
y. Put on pants								
z. Put on socks, shoes on both feet								
aa. Get in/out of bath or shower								
bb. Wash all parts of body								
cc. Get on/off the toilet								
dd. Feed yourself after food is readied								
ee. Groom yourself (brush hair and teeth)								
ff. Reach for an item on the ground from sitting position								

Post-Fracture Lower Extremity Physical Activities of Daily Living (LPADLs)

[only 12 items]

In this group of questions, I am interested in whether you had help in performing each of these activities.

By "help" I mean whether you used some device or equipment or the help of another person, to do the activity. Let me first give you some examples of what I mean when I ask whether you used equipment.

- To get dressed, some people use special dressing sticks or shoe horns.
- In the bathroom, raised toilet seats, bath seats, and grab bars in the toilet or tub are sometimes used.
- To reach things, you might use long-handled reachers.

Basically, I am interested in whether "in the past week" you used any devices or help from another person to perform these activities.

In the **PAST WEEK**, ON AVERAGE, did you use help to....

	No Help 0	Used Equip 1	Used Human Assist 2	Used Equip & Human Assist 3	Didn't perform: Health 4	Didn't perform: Non-health 5	Don't Know 7	Refused 8

m. Walk 10 feet or across a room								
If 1 or 3 selected indicate type of equipment  1=Cane(s) 2=Walker 3=Wheelchair 4=Crutches 5=Other								
n. Walk one block on a level sidewalk								
If 1 or 3 selected indicate type of equipment  1=Cane(s) 2=Walker 3=Wheelchair 4=Crutches 5=Other								
o. Climb 5 stairs								
p. Get into car								
q. Get in and out of bed								
r. Rise from an armless chair								
s. Put on pants								
t. Put on socks, shoes on both feet								
u. Get in/out of bath or shower								
v. Wash all parts of body								
w. Get on/off the toilet								
x. Reach for an item on the ground from sitting position								

Post-Fracture Instrumental Activities of Daily Living (IADLs)

I have a few more questions about common activities of daily life.

I would like to know if you did these activities during the PAST TWO WEEKS. For each activity, I'd like you to select the statement which best describes the amount of assistance you required to do each activity.

Q1. During the TWO WEEKS how did you usually get to places out of walking distance? Did you:

	1=Travel alone on buses, taxis, or drive your own car	Go to Q2
	2=Have someone to help you or go with you when traveling	Go to Q2
	3=Did not perform: health reason	Go to Q2
	4=Did not perform: non-health reason	Go to Q1a

Q1a. If you did not travel, could you travel:

	1=Independently
	2=With Assistance
	3=Would not be able to at all

Q2. During the PAST TWO WEEKS, assuming you had transportation, how did you usually go shopping for groceries or clothes? Did you:

	1=Take Care of all your shopping needs yourself	Go to Q3
	2= Have someone to go with you on all shopping trips	Go to Q3
	3=Did not perform: health reason	Go to Q3
	4=Did not perform: non-health Reason	Go to Q2a

Q2a. If you did not shop, could you shop:

	1=Independently
	2=With Assistance
	3=Would not be able to at all

Q3. During the PAST TWO WEEKS how did you usually prepare your meals? Did you:

	1=Plan and cook meals fully yourself	Go to Q4
	2=Prepare some things, but were unable to cook full meals yourself	Go to Q4
	3=Did not perform: health reason	Go to Q4
	4=Did not perform: non-health Reason	Go to Q3a

Q3a. If you did not prepare meals, could you prepare meals:

	1=Independently
	2=With Assistance
	3=Would not be able to at all

Q4. During the PAST TWO WEEKS how did you usually do your house cleaning? Did you:

	1=Do heavy work, such as scrubbing floors, by yourself	Go to Q
	2=Do light housecleaning, but had help with heavy work	Go to Q
	3=Did not perform: health reason	Go to Q
	4=Did not perform: non-health Reason	Go to Q4a

Q4a. If you did not house clean, could you clean:

	1=Independently
	2=With Assistance
	3=Would not be able to at all

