15.4 Short Physical Performance Battery

The short physical performance battery (SPPB) is a group of measures that combines the results of the gait speed, chair stand, and balance tests. It has been used as a predictive tool for possible disability and can aid in the monitoring of function in older people. The scores range from 0 (worst performance) to 12 (best performance). The SPPB has been shown to have predictive validity showing a gradient of risk for mortality, nursing home admission, and disability.

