15.4.2.3 Chair Stands

In this test, participants are first instructed to fold their arms across their chest and to try to stand up one time from an armless chair placed against a wall. To perform this test you will need a stopwatch and a straight-backed chair with a hard seat.

If the participant is successful rising from the chair once, they are then asked to stand up and sit down 5 times as quickly as possible. Timing begins as soon as the command to stand is given and continues until the participant straightens at the end of the fifth stand. When learning to do this, it is useful for two or more people to time the test so that the times can be compared for precision. For efficiency, it is valuable to have two chairs available so that the examiner can do the demonstration while the participant sits in the other chair and watches. If only one chair is available then the participant will have to get up to watch the demonstrations.

To ensure safety, the examiner should stand in front of the participant and be prepared to catch them if they fall forward. However, do not stand so close that the participant feels hemmed in and slows their pace during the chair stands.

1. Explain “*I want to see how long it takes you to stand up and sit down as quickly as possible 5 times without stopping. After standing up each time, sit down and then stand up again. Keep your arms folded across your chest. Please watch while I demonstrate. I’ll be timing you with a stopwatch*”
2. Demonstrate to the patient.
3. Ask the participant if they are ready. If so, begin timing as soon as they bend forward at the hips.
4. Count out loud the number of sits the participant has performed.
5. Stop the stop watch when they have sat down having completed the 5th stand. Also stop if the participant starts to use their arms, or after 1 minute they have not completed the test. Stop if the participant cannot complete 5 rises, and if you are concerned about the participant’s safety. Record the number of seconds and the presence of imbalance. Then complete scoring according to outcome measure template.

Your Health and Well-Being

This survey asks for your views about your health. This information will help keep track of how you feel and how well you are able to do your usual activities. *Thank you for completing this survey!*

For each of the following questions, please mark an in the one box that best describes your answer.

[figure not shown]
1. In general, would you say your health is:

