2.10.3.1.3. Short Physical Performance Battery

SPPB individual scores and total scores will be summarized using frequency counts and summary statistics. Observed values and change from baseline will be summarized.

Number and percent of subjects that:

- Improved by at least 1, 2 and 3 points,
- Whose total score is greater than 7, and
- Whose 4-meter gait speed increased by more than 0.1 m/sec

will be presented.

A Cochran-Mantel-Haenszel row mean score will be used to test for differences in frequency counts between treatment groups. An Analysis of Covariance with base value as a covariate and country as factor will be used to test for differences in the mean.

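### Protocol 15.4.2.3 gives two contradictory timing rules for the chair stand, so chair-stand times within the exploratory SPPB cannot be assumed comparable between assessors, sites or visits

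*Protocol*

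**What the plan says.** Protocol 15.4.2.3 describes the chair-stand timing twice.

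- **Introductory text:** "Timing begins as soon as the command to stand is given and continues until the participant straightens at the end of the fifth stand".
- **Numbered steps:** step 3 says to "begin timing as soon as they bend forward at the hips", and step 5 says "Stop the stop watch when they have sat down having completed the 5th stand".

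Step 5 ends with "Then complete scoring according to outcome measure template". That template is not part of the documents.

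Protocol 15.4 explains that the SPPB "combines the results of the gait speed, chair stand, and balance tests" into a score from 0 to 12. Protocol 6.8 schedules it at Randomization and at Visits 2, 3, 4 and 5, and on early withdrawal. Protocol 6.8.3 only refers back to Appendix 15.4.

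SAP 2.10.3.1.3 summarizes individual and total SPPB scores. It counts subjects who "Improved by at least 1, 2 and 3 points" and those with a total above 7, and it tests means with an ANCOVA that names baseline and country. It adds no timing rule. SAP 2.11 includes the SPPB in the Month 3 primary analysis, listed under exploratory objectives.

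**The concern.** Both descriptions are live instructions to sites. They disagree on when the clock starts and on when it stops, so two assessors who each follow the protocol can record different times for the same performance. If the rule applied to a subject changes between Baseline and Visit 4, the difference enters the change score directly with no change in the patient.

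Little in the plan would catch or absorb this. The instruction that one staff member should do a subject's serial tests is written for the 6MWT (Protocol 15.2), and staff certification is written for grip strength (Protocol 15.3). Neither is stated for the SPPB. The SPPB model in the SAP has no site or assessor term. With about 23 completers per arm now expected (SAP 2.14), avoidable measurement noise is unwelcome even in an exploratory endpoint.

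**Working it through.** **Step 1. Set the two rules side by side (Protocol 15.4.2.3).**

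| | Start | Stop |
|---|---|---|
| Introduction | command given | upright on stand 5 |
| Steps 3 and 5 | first hip bend | seated after stand 5 |

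Both events differ, and neither text is given precedence. The numbered steps are coherent among themselves: step 4 counts sits and step 5 stops on a sit. The introduction is equally complete. The one-minute limit in step 5 inherits the ambiguity, because whether the fifth repetition is finished in time depends on the stop rule.

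**Step 2. Look for a resolution elsewhere.** Protocol 6.8.3, Protocol 15.4 and SAP 2.10.3.1.3 give none. The balance and 4-meter walk procedures (Protocol 15.4.2.1 and 15.4.2.2) each have a single start and a single stop rule, so the problem is confined to the chair stand.

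**Step 3. Illustrate the size.** The documents give no chair-stand times, so these inputs are assumptions:

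- T, the time from first bend to upright on stand 5: 15 s or 20 s.
- r, the delay from command to first movement: 0.3 to 1.0 s.
- All rises and sits take equal time.

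To the fifth upright position there are 5 rises + 4 sits = 9 movements. To the fifth sit there are 5 + 5 = 10. The later stop therefore adds T/9: 15/9 = 1.67 s, or 20/9 = 2.22 s. The earlier start adds r.

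| Reading | Formula | T = 15 s | T = 20 s |
|---|---|---|---|
| Bend to upright (mixed) | T | 15.0 | 20.0 |
| Command to upright (introduction) | T + r | 15.3 to 16.0 | 20.3 to 21.0 |
| Bend to seated (steps) | T + T/9 | 16.7 | 22.2 |
| Command to seated (mixed) | T + T/9 + r | 17.0 to 17.7 | 22.5 to 23.2 |

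**Step 4. Compare the readings.**

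- Introduction against steps, each followed whole: (T + T/9) − (T + r) = T/9 − r.
  - At 15 s: 1.67 − 1.0 = 0.7 s to 1.67 − 0.3 = 1.4 s.
  - At 20 s: 2.22 − 1.0 = 1.2 s to 2.22 − 0.3 = 1.9 s.
- Shortest against longest, when the start is taken from one text and the stop from the other: T/9 + r.
  - At 15 s: 1.67 + 0.3 = 2.0 s to 1.67 + 1.0 = 2.7 s.
  - At 20 s: 2.22 + 0.3 = 2.5 s to 2.22 + 1.0 = 3.2 s.

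The plan states no figure on this point that could be reproduced. Its 84% and 99% power figures concern total lean body mass and do not depend on the SPPB.

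**The case against.** The best case for the plan accepts the contradiction and disputes its consequences.

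- **A single rule may be fixed elsewhere.** The scoring template, case report form or assessor training could settle the timing. A site that always uses one rule stays consistent with itself, and no document shows a switch or mixed practice. This stands, and it limits the claim to *cannot be assumed comparable*.
- **The differences offset.** A reader might infer that the stop rule adds about 11% and the start rule adds more on top. Between the two complete texts the reverse holds: the introduction starts earlier and the steps stop later, so the net gap is T/9 − r. The two add only when an assessor mixes the texts. This stands.
- **Seconds are not points.** The SAP analyses scores, and the time bands that convert seconds to points are not in the documents. How often 1 or 2 s changes a score, or moves a subject across a cut-off, cannot be stated. This stands.
- **The endpoint is exploratory.** A reader might infer a threat to the primary result because the SPPB is reported at the Month 3 primary analysis. The documents do not support that: SAP 2.11 lists it there as exploratory, and the primary endpoint is TBLH lean body mass by DXA. A reader might also infer a biased treatment comparison. Under double-blind randomization there is no reason to expect the choice of rule to follow treatment arm.

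None of this removes the contradiction or says which pair of rules governs.

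**Conclusion.** The point holds for the chair stand. Protocol 15.4.2.3 contains two incompatible start events and two incompatible stop events, and nothing in the documents reconciles them. This is an internal contradiction, not an omitted detail. Reading it as a fault in all SPPB timings would go too far, since the balance and walk timings each have one rule.

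The size is roughly 1 to 2 s between the two complete rules, and 2 to 3 s if they are mixed. Those figures rest on the assumed times, delay and equal-length movements. A longer delay would shrink the first gap, which vanishes when r = T/9 (1.7 s at T = 15 s, 2.2 s at T = 20 s).

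The expected effect is added noise in one of three components, with possible misclassification at the SAP's 1-, 2- and 3-point improvements and at the total above 7. Its frequency cannot be stated from the documents. The primary endpoint and the stated power are untouched. The correction is still worth making because it is specific and cheap.

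**What to change.** 1. Reconcile Protocol 15.4.2.3 to one start event and one stop event. Choose the pair that the scoring template assumes, so that times and score bands belong together, and delete the other pair.
2. Issue a short training note for the tests still to be done.
3. Before unblinding, which here means before the Month 3 primary analysis tables are produced by actual treatment group (SAP 2.11), document which rule each site used and flag tests timed otherwise. A reconciliation made after treatment results are known would be open to challenge.

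**Cost.** A minor amendment that needs sponsor and IRB approval (Protocol 11 and 12.2.1), plus the note. Two limits should be accepted. Enrollment was stopped early (SAP 2.14), so retraining may reach few remaining tests. Step 5 asks sites to record seconds and imbalance but not the timing rule, so flags on past tests may rest on site recall.

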1.1. Scope

This document contains detailed information to aid the production of the Clinical Study Report (CSR) including summary tables, figures, and listings for the Viking VK5211-201 trial. The contents of this document were reviewed by the sponsor, Viking Therapeutics, Inc., and the trial biostatistician at Integrium.

1.2. Study Overview

This is a phase II, randomized, double-blind, parallel group, placebo-controlled, multi-center study to investigate the safety, tolerability, and efficacy of VK5211 after 12 weeks of treatment.

Males and females \geq 65 years old who are ambulatory and recovering from a hip fracture will be eligible for participation 3-11 weeks post-injury.

After completing all Screening requirements, subjects will be randomized to one of four treatment arms (VK5211 0.5 mg, 1.0 mg, 2.0 mg, or placebo) in a 1:1:1:1 ratio and will receive their first dose of study treatment in the clinic.

The first bottle of study treatment will be dispensed and subjects will be instructed to take one oral dose of the assigned treatment at approximately the same time every morning, 30 minutes prior to breakfast.

Subjects will undergo safety and efficacy assessments as specified in the protocol on an approximately 4-week basis for a total treatment period of approximately 12 weeks. Following the 12-week treatment period, subjects will be followed for an additional 12-week period for assessment of safety and duration of drug effect.

During the study safety will be assessed on an ongoing basis by adverse events, identification of dose-limiting toxicities (DLTs) (if any), plasma concentrations, general physical examinations, vital signs, clinical laboratory assessments in blood, urine, as well as other specialized testing as required.

1.3. Study Objectives

1.3.1. Primary Objectives

The primary objective of this study is to determine the efficacy of VK5211 after 12 weeks of treatment by mean placebo-corrected percentage change in total body less head (TBLH) lean body mass assessed by whole body DXA scan.

1.3.2. Secondary Objectives

The secondary objectives of this study are:

- To assess the safety and tolerability of VK5211 after 12 weeks of treatment by comparing overall adverse events, vital signs, 12-lead ECG data, physical examinations, and hematology/chemistry/urinalysis data to placebo.
- To determine the efficacy of VK5211 after 12 weeks of treatment by mean placebo-corrected change in:
 - Hip bone mineral density (BMD) assessed by DXA
 - Total lean body mass (TLBM)
 - Appendicular lean body mass (ALBM)
 - Bone turnover markers (s-CTX and s-PINP)
- To assess plasma concentration of VK5211 near T_{max} and at trough levels in relation to total lean body mass.

1.3.3. Exploratory Objectives

The exploratory objectives of this study are to determine the efficacy of VK5211 compared to placebo after 12 weeks of treatment by:

- Physical Performance Assessments
 - 6 Minute Walk Test (6MWT) and BORG Scale
 - Grip Strength
 - Short Physical Performance Battery (SPPB)
- Patient Reported Outcomes
 - Pre- and Post-fracture Physical and Instrumental Activities of Daily Living (PADLs/IADLs)
 - Short Form-36 (SF-36)

2. Detailed Statistical Methods

2.1. General Statistical Methods

Efficacy analyses will be performed with both the Intent-to-Treat and Per Protocol Population. Safety analyses will be performed with the Safety Population. Data listings will be provided for all enrolled subjects.

All measured variables and derived parameters will be listed individually and, if appropriate, tabulated by descriptive statistics. For descriptive statistics, summary tables will include by treatment group summaries of sample size, arithmetic mean, standard deviation, coefficient of variation (if appropriate), median (and other percentiles, if appropriate), and minimum and maximum values. For categorical variables summary tables will include by treatment group summaries of frequency counts.

2.2. Study Populations

Safety Population:

All subjects who have taken a single dose of the study drug and provide follow-up information will be included in the safety population.

Intent-to-Treat (ITT) Population:

All subjects who have taken a single dose of the study drug and have a valid pre-baseline and post-baseline assessment will be included in the Intent-to-Treat population. Subjects will be analyzed as randomized, rather than as treated. This is the primary analysis population for assessing efficacy.

Per Protocol (PP) Population:

All Intent-to-Treat subjects who have taken at least 80% of the expected number of doses and do not have a major protocol violation will be included in the Per Protocol population. Subjects will be analyzed as treated, rather than as randomized.

Prior to unblinding, the exclusion of any subject from the Per Protocol Population will be documented including the reason for exclusion.

2.3. Definition of Baseline

In general, the study baseline is defined as the last observation obtained prior to the administration of the first randomized study medication, unless otherwise specified.

2.4. Subject Disposition and Characteristics

An account of the subjects by disposition will be tabulated overall. The number of subjects included in each analysis population will be summarized. Subjects not completing the study will be summarized and listed with the reason for their premature discontinuation. A list of screening failures will also be provided.

2.5. Demographics and Baseline Characteristics

Demographics and baseline characteristics will be presented using summary statistics (N, mean, standard deviation, median, minimum and maximum) for continuous measurements, or frequency tables (numbers and percentages) for categorical measurements, for the Intent-to-Treat, Per Protocol, and Safety Population.

2.6. Extent of Exposure and Compliance

For the 12-week treatment period, the number of days of exposure will be calculated as the number of capsules dispensed – the number of capsules returned.

The number of days of exposure to study medication and the percent compliance (number of days of exposure*100 / 84) will be summarized by treatment group using summary statistics (N, mean, standard deviation, median, minimum and maximum).

2.7. Prior and Concomitant Medications

Prior and concomitant medications will be coded using World Health Organization (WHO) Drug dictionary September 2015 version.

Prior medications will be defined as any medication that stops prior to the day of the first dose of study medication.

Concomitant medications taken at baseline will be defined as any medication that started on or prior to the baseline visit and stops on or after the day of the first dose of study medication.

Concomitant medications taken during treatment will be defined as any medication that stops on or after the day of the first dose of study medication, regardless of start date.

Section 2.14 describes the imputation rules for partial dates. Number and percentage of subjects receiving prior and concomitant medications will be summarized by treatment group and ATC classification (ATC level 2 and level 4) for the Safety Population. All medications will be presented in a data listing.

